## 21.0 Consent Process

### 21.1

 Obtaining Signed Consent (Subject or Legally Authorized Representative)	 Obtaining Consent Online (Waiver of Written Documentation of Consent )
 Obtaining Signed Parental Permission	 Obtaining Verbal Consent (Waiver of Written Documentation of Consent)
 Obtaining Signed Assent for Children or Adults Unable to Consent	 Waiving Consent and/or Parental Permission (Waiver of Consent Process)
 Obtaining Verbal Assent for Children or Adults Unable to Consent	 Waiving Assent/Assent is Not Appropriate

### 21.2

The signed consent will be used for Aim 2 for both EI providers and parents. The consent process will be completed remotely.

**EI provider consent process:** EI providers who are interested in the study will contact the PI or the project coordinator. The project coordinator or a trained research assistant

will schedule a phone or virtual Teams meeting to explain detailed research activities and go over the consent form together. The consent document will be emailed to each participant in advance and for them to keep. Once the project coordinator or the research assistant answer or clarify any questions that the provider has, the project coordinator/research assistant will send an electronic signature form to the provider via DocuSign.

**Parent consent process:** Parents will provide consent for study participation. Once EI providers indicate that one of their parents who have a child with or at risk/monitored for ASD and enrolled in the EI program is interested in participating in the study, the parent will contact the PI or the project coordinator to schedule a phone call or virtual Teams meeting. The project coordinator or a trained research assistant will explain detailed research activities and go over the combined parental consent and permission with the parents. The consent document will be emailed to each participant in advance and for them to keep. Once the project coordinator or the research assistant answer or clarify any questions that the parent has, the project coordinator/research assistant will send an electronic signature form to the parent via DocuSign.

Aim 2 research activities explained in the consent form:

- EI providers: signed consent form
  - Attending training sessions
  - Implementing intervention
  - Completing fidelity checklist
  - Exit interview virtually through Microsoft Teams
- Parents: signed consent form
  - Dietary intake assessment virtually through Microsoft Teams
  - Mealtime behavior, demographic, and health conditions questionnaires through online survey platform (REDCap)
  - Height and weight measurement
  - Exit interview virtually through Microsoft Teams

21.3

The consent online (waiver of written documentation of consent) will be used for aim 1 for both EI providers and parents.

EI providers and parents who are interested in the study will contact the PI or the project coordinator. The project coordinator or a trained research assistant will assess the eligibility and explain the study procedure via a preferred method by the participant (e.g., email, phone call, virtual meeting), and send the REDCap survey link to the participant including the consent document. Participants will be asked to proceed with the survey by clicking the “next” button on the page if they agree to participate, or they will be asked to

leave the survey page. All participants will have access to the copy of consent document via email, REDCap, or file attachment in the virtual meeting.

Aim 1 research activities explained in the consent form:

- EI provider/parent manual review. Feedback from the EI providers and parents will be collected through online survey platform (REDCap)

21.4 N/A

21.5 Once the English consent document is approved by the IRB, the study team will submit an amendment to obtain approval for the Spanish consent document. The Spanish-speaking research staff will be responsible for translating the consent from English to Spanish. A separate independent translator who has no knowledge of or contact with the original text will translate the consent back from Spanish to English. The project coordinator or trained research assistant will then assess the two versions to see if they are consistent. Approved translated consent form will be used by the Spanish-speaking research staff to obtain consent from all Spanish-speaking participants.

21.6 The children to be enrolled are from birth to 36 months diagnosed with or at risk/monitored for ASD status and cannot provide consent. Parental permission will be obtained from parent participants.

## **22.0 Setting**

22.1 The study will be conducted at the USF College of Public Health (single site). The Florida EI service is called Early Steps. There are 15 Early Steps programs in Florida and the USF Early Steps program covers two counties (Hillsborough and Polk Counties). EI providers and parents from the USF Early Steps program in these two counties will be recruited for both Aim 1 and 2 of the study. For Aim 2, participants will be involved in weekly Autism Eats sessions or one EUC session through their regular EI services. The EI providers from the USF Early Steps program will be recruited on a rolling basis and parent-child dyads will be recruited through those EI providers. The director of the USF Early Steps program is a Co-investigator of the project ([name]) and there will be a project liaison staff person who will be paid to assist with the study recruitment and communication. [name] participated in protocol writing and has attended monthly project meetings since August 2021. All decisions regarding recruitment and participant engagement have been discussed with [name] and approved by her. Any further changes will be discussed with [name] at regular research team meetings.

Title: *An integrated nutrition intervention through the Part C Early Intervention Services to promote healthy eating habits for children with ASD.*

NCT number: NCT05194345

Document date: 10/24/2022

STATISTICAL DESIGN AND POWER

DATA COLLECTION, DATA MANAGEMENT, AND RANDOMIZATION

All the data will reside at the College of Public Health. The PI and [name] (Co-I statistician) will ensure the confidentiality of the data at all times. Participants will be assigned a participant ID (PID) at the time of screening. The PID will be a unique 8-digit number that includes a check digit. Access to the computer at the PI's office both internally and externally will be restricted by using individual user accounts and passwords. Study participants will be randomized after collection of the baseline data. [name] will design the randomization, and a data entry and management system for this project. We will use Research Electronic Data Capture (REDCap™), a widely used secure web-based software package designed for clinical trials.

SAMPLE SIZE CALCULATION AND POWER ANALYSIS

We will enroll a total of N=30 EI providers and parent-child dyads with a 1:1 randomization between Autism Eats intervention and Enhanced Usual Care (EUC) comparison group. The sample size calculation is not required for this pilot study. While evaluation of outcomes is more appropriate for a fully-powered R01, we will examine variance and effect sizes of key outcomes from pre- to post-intervention, and post-intervention to 5-month follow-up using non-parametric tests and confidence intervals.

DATA ANALYSIS

Descriptive analyses of baseline characteristics and outcomes will include means and standard deviations for continuous variables and frequencies for categorical variables. Treatment compliance will also be evaluated. The primary analysis will be conducted based on the intent-to-treat principle. Distributional assumptions will be checked and appropriate transformations or non-parametric methods will be applied as necessary.

Specific Analyses for the Individual Study Aims:

Aim 2a. Test the feasibility of enrollment, implementation, and evaluation of Autism Eats. We hypothesize that Autism Eats will be feasible and well received by EI providers and parent-child dyads, which will be assessed with (1) reach/participation; (2) attrition; (3) completion; (4) fidelity; (5) compatibility; and (6) qualitative feedback from participants. The rates of reach, participation, attrition, and completion will be computed as described in the measures section. Descriptive statistics will be used to examine data distributions and frequencies. If there is substantial variability in attrition, completion, fidelity, and compatibility, we will examine the relations of such variables with any other variables we collect during the study such as demographic variables of EI providers and parent-child dyads. (See Table 3).

Table 3. Benchmarks for Feasibility

Indicators	Measures and Benchmarks
Reach/Participation	Tracking log. >75% of approached eligible providers and parent-child dyads agree to participate (until n=30 parent-child dyads recruited)
Attrition	Tracking log. <20%
Completion	Lesson completion checklist, assessment tracking sheets, and attendance records. >75%
Fidelity	Lesson observations – 5-point scale (5=completed with fidelity; 1=not completed at all) per lesson. Mean >3.0
Compatibility	Observations & provider interviews. Qualitative coding: positive feedback.
Participant feedback	Provider and parent interviews. Qualitative coding: positive feedback.

Aim 2b. To assess the preliminary efficacy of Autism Eats on child dietary intake and mealtime behaviors.

While evaluation of outcomes is more appropriate for a fully-powered R01, we will examine variance and effect sizes of key outcomes from pre- to post-intervention, as well as post-intervention to 5-month follow-up using non-parametric tests and confidence intervals. We expect differences in children's food intakes, variety, diet quality,⁹ and mealtime behaviors¹⁶ between children who participate in Autism Eats and those in the EUC groups at post-intervention and 5-month follow-up from baseline. We will first assess whether

Autism Eats and EUC groups are balanced through randomization in terms of demographic variables at baseline. For each outcome variable, we will use boxplots and scatterplots with confidence intervals to visually inspect the changes across pre-intervention, post-intervention, and 5-month follow-up by group along with descriptive statistics. Also, nonparametric longitudinal analysis will be conducted for each outcome variable with time as a within-subject factor and treatment condition as a between-subject factor to examine the difference in changes between Autism Eats and EUC groups. (See Table 4).

Exploratory Aim. We will explore whether weight status of children are different between Autism Eats and EUC groups at 5-month follow-up assessment. Descriptive statistics and visual inspection will be used to summarize weight status by group and effect sizes will be computed. Similar to the analysis of the primary outcomes, we will conduct nonparametric analysis to compare the changes in weight status at 5-month follow-up between Autism Eats and EUC groups. Note that parent BMI will be included as a covariate in the analysis.

Table 4. Efficacy Outcomes

Outcomes	Measures / Expected Outcomes	Time
Dietary intake	3-day food records (ASA24 TM) / Food intakes (e.g., fruit and vegetables ↑), daily food variety ↑, diet quality (e.g., HEI fruit ↑, vegetables ↑, plant protein ↑)	T1, 2,3
Mealtimes behaviors	Brief Autism Mealtime Behavior Inventory ¹⁶ via REDCap / Problematic behaviors ↓.	T1,2,3
Weight status (height and weight)	A stadiometer/ruler and a scale; birth to 36 months, weight-for-length%tile based on the CDC growth chart. ¹⁷ BMI for parents	T1 & 3
Demographics	A survey through the REDCap.	T1
Health conditions	Family history of ASD and comorbid health conditions such as epilepsy, sleep disorders, and anxiety disorders through the REDCap.	T1

Biological variables. Sex: Given the sex difference in ASD prevalence, in addition to the primary data analyses as described above, data distributions will be analyzed by sex. We will then explore how male and female students respond to our intervention differently through qualitative interviews with selected sub-samples. Recommendations will be created to address any sex differences.

Genetic factors: Family history of ASD and parent BMI will be measured and considered as covariates.

Potential confounding factors to be considered in the analytic models. Parent age, sex, race/ethnicity, baseline child's weight status, parent education, and family income.

Examine demographic variations in response to the Autism Eats intervention. Correlation will be used to examine associations between demographic variations (age, sex, race/ethnicity, SES, and baseline weight status) outcomes of the Autism Eats (food intakes, food variety, diet quality, mealtime behaviors, and weight percentile).

Attrition and Missing Data. See Benchmarks for feasibility (Table 3). We aim < 20% dropout due to study withdrawal. Every effort will be made to prevent dropouts/missing data, and to complete relevant assessments for participants who drop out or are withdrawn, including reasons why the intervention was ended. To handle the dropout problem in this trial, we will first analyze data to see whether dropout was related to certain baseline measures and demographic variables. We will report the dropout rate and compare the distributions of baseline measures and demographic variables.

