**REVISION HISTORY**

**\*This table should only be used during submission of a Modification application to the IRB.**

Revision #	Version Date	Summary of Changes	Consent Change?
2	01/23/2022	
 
• Data sharing agreement added, complying with the NIH requirement (Section 16.). Parent consent form has been updated to include this data sharing details. This does not impact the EI providers' consent.
 
• Recruitment email address change on recruitment letters.
 
• Height and weight measurement procedure and exit interview guides have been modified to improve clarity.
 
	Yes
3	09/21/2022	
 
• Eligibility criteria for the parent-child dyads has been updated
 
• The timing of asking the autism spectrum disorder (ASD) diagnosis or at risk/monitored for ASD status has been updated by adding another time point at the 5-month follow-up assessment
 
• The health conditions questionnaire timing has been updated to add “T3” – follow-up time point (Table 4. in Section 5.7). A short self-report questionnaire with the same 4 items on health conditions/medications
 
	Yes

		
assessed at baseline through the demographic questionnaire will be used
 
 
• Consent forms have been updated to reflect the eligibility criteria and the timing of asking the ASD diagnosis or at risk/monitored for ASD status
 
• A new recruitment flyer is added for the Early Steps to use on their Facebook page
 
• ClinicalTrials.gov registration number has been updated
 
	
--	--	--------------------------------------------------------------------------------------------------------------------------------------------------------------------------------------------------------------------------------------------------------------------------------------------------------------------------------------------------------------------------------------------------------------------------------------------------------	--

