## 1.0 Study Summary

Study Title	An integrated nutrition intervention through the Part C Early Intervention Services to promote healthy eating habits for children with ASD
Study Design	Randomized controlled trial
Primary Objective/Purpose	Aim 1: To refine the Autism Eats manual and intervention materials. Aim 2: To evaluate the feasibility and preliminary efficacy of Autism Eats in improving dietary intake and mealtime behaviors of children with ASD.
Secondary Objective(s)/Purposes	To explore whether child weight status differs between Autism Eats and enhanced usual care groups at 5-month follow-up assessment.
Research Intervention(s)	Autism Eats – Early childhood nutrition intervention
ClinicalTrials.gov NCT #	NCT05194345
Study Population	Early intervention providers and parent-child dyads (child aged 0-36 months clinically diagnosed with ASD)
Sample Size	146 individuals Aim 1: 10 EI providers, 10 parents Aim 2: 30 EI providers, 48 parent-child dyads (48 parents and 48 children)
Study Duration for individual subjects	Aim 1: up to 3 hours per participant to review manual and provide feedback. Aim 2: Parent-child dyads : The Autism Eats intervention group will spend about 8.5 hours over 5 months (baseline, post intervention, and 5-month follow-up assessments are 30 minutes each, 25-30 minutes weekly sessions for up to 10 weeks, two 25-30 minutes monthly booster sessions, and a 60-minute exit interview), and the We Can! EUC control group will spend about 3 hours over 5 months (baseline, post intervention, and 5-month follow-up assessments are 30 minutes each, one 25-30 minute nutrition session, and a 60-minute exit interview). EI provider : The Autism Eats intervention group EI provider will spend about 12 hours over 5 months (two 90-minutes training sessions, 25-30 minutes weekly sessions for up to 10 weeks, two 25-30 minutes monthly booster sessions, 10-minute fidelity checklist completion

	after each session, and a 60-minute exit interview), and the We Can! EUC control group EI provider will spend about 4.5 hours over 5 months (two 90-minutes training sessions, one 25-30 minutes session, 1-2-minute written material distribution at their 9 weekly EI sessions, and a 60-minute exit interview).

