## 5.0 Procedures Involved

### 5.1

Aim 1: The EI providers (n=10) and parents (n=10) will be invited to review the intervention manual and materials and provide their feedback. Participants will receive a survey link for the manual review which is described in 5.2 below. Based on the results of the review, all intervention materials will be further refined and finalized.

Aim 2: The protocol for this project is designed to conduct a preliminary RCT. This pilot RCT compares Autism Eats (n=24 parent-child dyads) to the EUC condition using We Can! materials (n=24 parent-child dyads). EI providers (n=30) in two Florida counties (Hillsborough and Polk Counties) will be recruited on a rolling basis and parent-child dyads will be recruited through those EI providers. Baseline assessment will be scheduled. Study participants will be randomized into two intervention groups (Autism Eat and EUC We Can!) after collection of the baseline data. Random assignment will be conducted by [name] (Co-I) utilizing a random number generator. Participants in Autism Eats will receive the intervention components while those in the EUC group receive comparison We Can! materials. Data collection will be performed at three time points. Study design is also described in Figure 1.

5.2

 Audio/Video Recording	 Psychophysiological Recording
 Behavioral Interventions	 Record Review - Educational
 Behavioral Observations and Experimentations	 Record Review - Employee
 Deception	 Record Review- Medical
 Focus Groups	 Record Review - Other
 Interviews	 Specimen Collection or Analysis
 Investigational Device – Non-Significant Risk (e.g. Mobile Applications)	 Surveys and/or Questionnaires
 Psychometric Testing	 Other Social-Behavioral Procedures

**Aim 1:** We will invite EI providers and parents to review the intervention manual and materials and provide their feedback. The review invitation will be sent out through an online survey link (RedCap).

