For EI providers, the feasibility scale used in our pilot study will be used. Seven questions will address feasibility of implementing each lesson, clarity of instructions, relevance to the EI services, acceptability by parents, satisfaction of resources/references, and clarity and relevance to the overall goal. Open-ended questions on each lesson will allow EI providers to share recommendation regarding each session's content and materials. The manual review will take up to 3 hours per participant.

For parents, the feasibility scale will be tailored to parent participants and address clarity of instructions, acceptability, satisfaction of intervention materials, and feasibility of implementing feeding practices at home. Open-ended questions on each lesson will allow parents to share recommendation regarding each session's content and materials. The survey will take about 1-2 hours per participant.

**Aim 2:** We will track the number of EI providers and parents reached by the recruitment methods. We will monitor and document reasons for dropping out, and clearly indicate whether it was the provider or the parent who decide to drop out. Completion rates of assessments at all data collection time points, training sessions, and lesson and booster lesson implementation will be tracked and recorded.

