## **11.0 Local Number of Subjects**

11.1

For Aim 1, 10 EI providers and 10 parents will be enrolled.

For Aim 2, 30 EI providers and 48 parent-child dyads (48 parents and 48 children) will be enrolled.

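### The SAP counts recruitment to 30 parent-child dyads, the protocol enrols 48 (24 per arm), and nothing reconciles the two

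*SAP*

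**What the plan says.** **SAP.** Table 3 (Benchmarks for Feasibility), Reach/Participation row, sets an agreement rate above 75% among eligible providers and dyads approached, counted "until n=30 parent-child dyads recruited". The section on sample size and power says "We will enroll a total of N=30 EI providers and parent-child dyads with a 1:1 randomization" between the two groups, and adds that a pilot needs no sample size calculation. The number 48 does not appear in the SAP.

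**Protocol.** Section 1.0 gives the sample as "146 individuals Aim 1: 10 EI providers, 10 parents Aim 2: 30 EI providers, 48 parent-child dyads (48 parents and 48 children". Section 5.1 gives the arms: "This pilot RCT compares Autism Eats (n=24 parent-child dyads) to the EUC condition using We Can! materials (n=24 parent-child dyads". The same section attaches 30 to the providers: "EI providers (n=30) in two Florida counties (Hillsborough and Polk Counties) will be recruited on a rolling basis". Section 11.1 repeats the plan: "For Aim 2, 30 EI providers and 48 parent-child dyads (48 parents and 48 children) will be enrolled". On reach, section 5.2 says only "We will track the number of EI providers and parents reached by the recruitment methods", with no threshold. The 75% benchmark exists only in the SAP.

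**The concern.** The number of dyads randomised is a basic design parameter, and the two documents that govern the trial give different values for it. The conflict is between the SAP's recruitment count and the protocol's enrolment number. It is not between two benchmarks, since the protocol sets none for reach.

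A team working from SAP Table 3 could treat dyad recruitment as complete 18 dyads short of the protocol. Feasibility of enrolment is itself an aim (Aim 2a). If 30 dyads were enrolled, a later reader could not tell whether the trial had met its plan or fallen 37.5% below it.

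**Working it through.** **Inputs**

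| Quantity | Value | Source |
|---|---|---|
| Aim 1 participants | 10 providers, 10 parents | Protocol 1.0, 11.1 |
| Aim 2 providers | 30 | Protocol 1.0, 5.1, 11.1 |
| Aim 2 dyads | 48 (24 per arm) | Protocol 1.0, 5.1, 11.1 |
| Total individuals | 146 | Protocol 1.0 |
| Dyads in the reach benchmark | 30 | SAP Table 3 |
| Allocation | 1:1 | SAP, sample size section |
| Dropout limit | below 20% | SAP Table 3 and missing-data paragraph |

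**1. Reproduce the protocol's figures.** Each dyad counts as two individuals.

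- Arms: 24 + 24 = 48, as stated.
- Total: 10 + 10 + 30 + 48 + 48 = 146, as stated.

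**2. Put in 30 dyads, keeping 30 providers.**

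- Total: 10 + 10 + 30 + 30 + 30 = 110, which is 36 below 146.
- Aim 2 alone: 30 + 30 + 30 = 90, against 30 + 48 + 48 = 126.
- Per arm at 1:1: 30 / 2 = 15, against 24. The SAP does not state 15; it follows from the ratio.
- Gap: 48 − 30 = 18 dyads; 30/48 = 62.5%; 48/30 = 1.6.

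**3. Could 48 be 30 inflated for dropout?**

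- 30 / (1 − 0.20) = 37.5, rounded up to 38.
- Multiplying by 1.20 instead gives 36.
- Getting from 30 to 48 needs a dropout of 1 − 30/48 = 37.5%, well above the 20% limit.
- In the other direction, 48 × 0.80 = 38.4 completers, not 30.

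Dropout does not link the two numbers.

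**4. Could the SAP sample size sentence mean 48 dyads?** It can be read as 30 of each, as 30 in total, or as 30 providers plus an unstated number of dyads. None of these readings states 48. The third leaves the SAP's sample size section with no dyad number and does not help Table 3, which names dyads explicitly.

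**5. Is 30 a later decision?** The SAP is dated 10/24/2022, after protocol revision 3 of 09/21/2022, so its date alone might suggest so. But revision 3 records "The health conditions questionnaire timing has been updated to add" the 5-month follow-up (T3). Protocol Table 4 shows that change (T1 and T3), while SAP Table 4 still lists health conditions at T1 only. The SAP therefore does not carry all of revision 3, and its later date does not show that 30 replaced 48. No revision entry mentions sample size.

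**6. What the difference would mean for estimation (illustration only).** Assume a standardised outcome (SD 1), independent dyads and a normal approximation; none of this is in the documents. The 95% interval half-width for a between-arm difference is 1.96 × √(2/n), with n per arm.

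| | 30 dyads | 48 dyads |
|---|---|---|
| No dropout | n = 15: 0.72 | n = 24: 0.57 |
| 20% dropout | n = 12: 0.80 | n = 19: 0.64 |

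The conclusion does not depend on this table.

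**The case against.** The strongest reply is that Table 3 lists feasibility benchmarks and is not an enrolment or stopping rule. On that view the 30 only marks the window over which the agreement rate is counted, inside a trial of 48 dyads. If the 30 in the sample size sentence is then taken as the provider count, the SAP omits 48 without contradicting it. No text supports such a window, and the reading sits badly with a sentence that speaks of enrolling a total of 30. It does mean that an early stop is a possible consequence of Table 3, not a certain one.

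Protocol text also makes an early stop less likely. Section 11.1 states how many will be enrolled, section 12.2 keeps distributing recruitment materials until the target is met (in its provider paragraph), and section 16.3 reviews accrual monthly against the protocol. This stands as mitigation, but none of it explains the 30.

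The effect on inference is limited too. The documents state no power or precision target, and no analysis method or outcome definition changes with the dyad number. That is conceded.

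Other signs that the SAP may carry older text are weak. Its Table 4 lacks the protocol's feeding behaviours row, and Aim 2a points to a measures section that the SAP does not contain. Neither bears on 30 versus 48. Only the health-conditions timing helps with document order, and even that does not prove carry-over.

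**Conclusion.** The concern holds. The planned number of dyads is 48 in the protocol and 30 in SAP Table 3, a difference of 18 dyads, or 36 individuals if providers stay at 30. On the dyad count the protocol agrees with itself in three sections and with its own total; the SAP figure fits none of these. Dropout, revision history and document dates do not reconcile them. Which number is intended, and how 30 entered the SAP, cannot be settled from the documents.

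This must be fixed because the two governing documents disagree on trial size. It is not a finding about power, and it leaves the percentage benchmarks as they are. The result rests on head counts; the only derived design figure is 15 per arm, which assumes 1:1 allocation of 30 dyads.

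**What to change.** The sponsor should confirm the intended number of dyads.

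- **If 48 stands**, as the protocol's dyad counts indicate: revise the SAP sample size section to give 48 dyads (24 per arm) and 30 providers, and change the count in the Table 3 reach row from 30 to 48. This is two wording edits, with no new data or analysis.
- **If 30 was deliberate**: it is a change of design. Record the decision and its reason, and amend at least protocol sections 1.0 (including the total of 146), 5.1 and 11.1. That is a protocol amendment to planned enrolment.

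In both cases the SAP should state providers and dyads as separate numbers. If Table 3 was meant to measure reach over only the first 30 dyads, it should say so explicitly.
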